11.2 Analysis Plan for Endpoints

11.2.1 Primary Endpoint:

The primary endpoint of the MPR proportion will be calculated for both treatment arms and 80% one-sided confidence intervals will be estimated via binomial proportions. The chi-square test or Fisher's exact test will be used, as appropriate, to compare the MPR proportions between the two arms. We will also generate the odds ratio and a corresponding 95% confidence interval to contrast the difference in MPR proportions between the two arms. Logistic regression will be used to generate the odds ratio and corresponding CI.

11.2.2 Secondary Endpoints:

The first secondary endpoint of 2-year DFS proportion will be calculated for the pooled group of patients (N=60) and a 95% confidence interval will be estimated via binomial proportions. An additional calculation will also be stratified by Arm 1 vs. Arm 2. The chi-square test or binomial exact test, whichever is appropriate, will be used to compare the 2-year DFS proportion in the 60 patients to the historical 2-year DFS proportion of 75%. The chi-square test or Fisher's exact test will be used, as appropriate, to compare the 2-year DFS proportion between the two arms.

The clinical response proportion will be calculated for both treatment arms and 95% confidence intervals will be estimated via binomial proportions. The chi-square test or Fisher's exact test will be used, as appropriate, to compare the clinical response proportions between the two arms.

The safety of durvalumab with and without low dose SBRT in the neoadjuvant setting in NSCLC will be investigated. All AEs in both arms \geq G3 with and without possible or probable attribution to study drug will be tabulated. The frequency of subjects experiencing toxicities will be tabulated for each arm. Toxicities will be assessed and graded according to CTCAE v. 4.0 terminology. Exact 95% confidence intervals around the toxicity proportions will be calculated to assess the precision of the obtained estimates. All analyses will be performed in SAS Version 9.4 (SAS Institute, Inc., Cary, North Carolina) and STATA Version 13.0 (Stata Corporation, College Station, Texas).

DFS will also be estimated using the Kaplan-Meier method, and 95% confidence intervals for DFS estimates will be calculated using Greenwood's formula. Median DFS will also be estimated along with a 95% confidence interval. These calculations will also be stratified by Arm 1 vs. Arm 2 for the purpose of the secondary aim. The log-rank test will be used to compare Kaplan-Meier DFS between the two arms (for exploratory purposes only; this comparison will not be statistically powered to detect specific differences between the two arms).

REFERENCES

2. Arriagada, R. et al. Long-term results of the international adjuvant lung cancer trial evaluating adjuvant Cisplatin-based chemotherapy in resected lung cancer. *JCO* 28, 35-42, (2010).
4. Douillard, J. Y. et al. Adjuvant vinorelbine plus cisplatin versus observation in patients with completely resected stage IB-IIIa non-small-cell lung cancer: a randomised controlled trial. *The Lancet. Oncology* 7, 719-727,(2006).
5. Strauss GM, Herndon JE 2nd, Maddaus MA, Johnstone DW, Johnson EA, et al. Adjuvant paclitaxel plus carboplatin compared with observation in stage IB non-small-cell lung cancer: CALGB 9633 with the Cancer and Leukemia Group B, Radiation Therapy Oncology Group, and North Central Cancer Treatment Group Study Groups. *J Clin Oncol*. 2008 Nov 1;26(31):5043-51.
7. Kiankhooy, A. et al. Predictors of early recurrence for node-negative t1 to t2b non-small cell lung cancer. *The Annals of thoracic surgery* 98, 1175-1183, (2014).
8. Radiant Trial. A randomized, double-blind phase 3 trial of adjuvant erlotinib versus placebo following complete tumor resection with or without adjuvant chemotherapy in patients with stage IB-IIIa EGFR positive NSCLC ASCO (2014).

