3.0 PATIENT SELECTION

3.1 Inclusion Criteria

1. Patient has histologically or cytologically proven clinical stages I (tumors > 2 cm), II, and IIIA NSCLC and is considered eligible for surgical resection with curative intent. Patients with 2 primary non-small cell lung cancers are allowed.
2. Measureable disease, as defined by RECIST v1.1.
3. Written informed consent and HIPAA obtained from the subject prior to performing any protocol-related procedures.
4. Age ≥ 18 years at time of study entry
5. Eastern Cooperative Oncology Group (ECOG) performance status of 0 or 1.
6. Adequate normal organ and marrow function as defined below:
 - Haemoglobin ≥ 9.0 g/dL
 - Absolute neutrophil count (ANC) ≥ 1.5 x 10⁹/L (> 1500 per mm³)
 - Platelet count ≥ 100 x 10⁹/L (>100,000 per mm³)
 - Serum bilirubin ≤ 1.5 x institutional upper limit of normal (ULN). This will not apply to subjects with confirmed Gilbert’s syndrome (persistent or recurrent hyperbilirubinemia that is predominantly unconjugated in the absence of hemolysis or hepatic pathology), who will be allowed only in consultation with their physician.
 - AST (SGOT)/ALT (SGPT), and alkaline phosphatase ≤ 2.5 x institutional upper limit of normal (ULN).
 - Serum creatinine CL>30 mL/min by the Cockcroft-Gault formula (Cockcroft and Gault 1976) or by 24-hour urine collection for determination of creatinine clearance:

Males:

$$\text{Creatinine CL (mL/min)} = \frac{\text{Weight (kg)} \times (140 - \text{Age})}{72 \times \text{serum creatinine (mg/dL)}}$$

Females:

$$\text{Creatinine CL (mL/min)} = \frac{\text{Weight (kg)} \times (140 - \text{Age})}{72 \times \text{serum creatinine (mg/dL)}} \times 0.85$$

7. Evidence of post-menopausal status or negative urinary or serum pregnancy test for female pre-menopausal patients. Women will be considered post-menopausal if they have been

amenorrheic for 12 months without an alternative medical cause. The following age-specific requirements apply:

Women <50 years of age would be considered post-menopausal if they have been amenorrheic for 12 months or more following cessation of exogenous hormonal treatments and if they have luteinizing hormone and follicle-stimulating hormone levels in the post-menopausal range for the institution or underwent surgical sterilization (bilateral oophorectomy or hysterectomy).

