4.2 Randomization

Blocked randomization will be performed for the secondary aim. A series of randomized blocks of 4 will be generated with a 1:1 allocation ratio. This will provide assurance that after four patients are enrolled in the study, there will be two patients assigned to the antibody + radiation arm and two patients assigned to the antibody + no radiation arm. This procedure will allow for a similar number of antibody + radiation patients (Arm 2) and antibody + no radiation patients (Arm 1).

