9.0 MEASUREMENT OF EFFECT

9.1 Assessment of disease-free survival

All patients will be followed in our thoracic oncology follow-up clinic for disease recurrence using history, physical examination and CT scanning every 6 months for 2 years. This follow-up protocol represents our institutional standard of care. Recurrence will be histologically or cytologically confirmed whenever possible. For the purpose of this trial DFS is defined as confirmed disease recurrence or death from any cause.

9.2 Assessment of clinical response.

All patients will have pre-treatment and post-treatment standard imaging including a positron emission tomography (PET)/computerized tomography scan (PET/CT scan) to determine disease stage and assess response to therapy. All imaging will be downloaded to our imaging data evaluation and analysis laboratory (IDEAL); a state of the art imaging facility operated by the Weill Cornell Department of Radiology. Independent radiologists blinded to treatment allocation will assess tumor shrinkage using conventional RECIST criteria 1.1.

Complete Response (CR): Disappearance of all target lesions. Any pathological lymph nodes (whether target or non-target) must have reduction in short axis to <10 mm.

Partial Response (PR): At least a 30% decrease in the sum of diameters of target lesions, taking as reference the baseline sum diameters.

Progressive Disease (PD): At least a 20% increase in the sum of diameters of target lesions, taking as reference the smallest sum on study (this includes the baseline sum if that is the smallest on study). In addition to the relative increase of 20%, the sum must also demonstrate an absolute increase of at least 5 mm. (Note: the appearance of one or more new lesions is also considered progression).

Stable Disease (SD): Neither sufficient shrinkage to qualify for PR nor sufficient increase to qualify for PD, taking as reference the smallest sum diameters while on study.

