11. STATISTICAL CONSIDERATIONS

11.1 Specific Aims

11.1.1 Primary Aim:

The primary aim of this study is to determine that subablative SBRT at a dose of 8Gyx3 given concurrently with neoadjuvant durvalumab will increase the major pathological response (MPR) proportion from an estimated 15% in Arm 1 (Durva alone) to 35% in Arm 2 (SBRT+Durvalumab). A two-group chi-square test with a 0.20 one-sided significance level will have approximately 83% power to detect the difference between the Arm 1 MPR proportion of 0.15 and the arm 2 MPR proportion of 0.35 when the sample size is 30 in each arm.

11.1.2 Secondary Aim:

The first secondary aim of this study is to demonstrate that the use of durvalumab (with/without radiation) is associated with an improvement in the 2-year disease-free survival (DFS) proportion from 75% (historical control) to approximately 88% with the use of the new antibody. The historical control rate was determined from the DFS rate reported by Strauss et al from CALGB 9633, a US based randomized trial of adjuvant chemotherapy versus observation in patients with pathological stages IB and II NSCLC³⁴. The reported 2-year DFS was 68% in the observation arm and 75% in the chemotherapy arm³⁴. Our institutional data are consistent with these results. Among patients in our database who were assigned a clinical stage, there were 215 patients with clinical stages IB and II some of whom received adjuvant chemotherapy. DFS for these 215 patients is shown in Figure 2 and was 75% at 2 years. We did not use DFS reported from other randomized trials since these were international trials and approximately 20-25% of patients enrolled had stage IIIA disease. In our proposed trial, an improvement in DFS by 13% (75% to 88% at 2 years) represents a 17% relative improvement in DFS; a difference that we believe to be both achievable and clinically meaningful. These results will necessarily lead to larger randomized trials for further confirmation.

Another secondary aim is to compare the clinical response between patients receiving the durvalumab alone (Arm 1) and patients receiving the antibody with radiation (Arm 2). Assuming clinical response proportions of 15% and 35% in Arms 1 and 2, respectively, 95% confidence intervals for the clinical response proportions can be constructed to be within $\pm 12.8\%$ and $\pm 17.1\%$ of the observed clinical response proportions in each arm, respectively.

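### Neither the randomisation nor the MPR comparison uses clinical stage, so the plan has no pre-specified remedy for a chance stage imbalance; this is a conditional risk, not a bias

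*Combined protocol and SAP*

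**What the plan says.** Section 4.2 describes the allocation: "A series of randomized blocks of 4 will be generated with a 1:1 allocation ratio". It names no stratification factor.

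Section 11.2.1 tests MPR between arms with a chi-square or Fisher's exact test. The odds ratio comes from a separate model: "Logistic regression will be used to generate the odds ratio and corresponding CI". No covariate is named for that model. Section 11.2.2 compares clinical response with the same unstratified tests. In Section 11.2, stratification only ever means reporting by arm, and no stage-adjusted or sensitivity analysis of MPR is planned.

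Stage is available throughout. Section 3.1 makes it an eligibility item: "Patient has histologically or cytologically proven clinical stages I (tumors > 2 cm), II, and IIIA NSCLC". Section 9.2 has every patient imaged before treatment "to determine disease stage and assess response to therapy". The stratum is therefore known before the allocation is drawn.

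**The concern.** The trial enrols a wide stage range and randomises only 60 patients. Blocks of 4 keep the arm totals equal but do nothing to keep the stage mix equal. If stage is related to pathological response and the arms happen to differ in stage, part of the observed MPR difference reflects stage, not radiation, and nothing in the plan removes that part.

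The practical stake is credibility. The trial is open label with a one-sided level of 0.20. If the arms come out unbalanced, any stage adjustment would have to be chosen after the results are known, and a reader could dispute the choice either way.

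**Working it through.** **1. The plan's own figure.** Section 11.1.1 states: "A two-group chi-square test with a 0.20 one-sided significance level will have approximately 83% power", for an "Arm 1 MPR proportion of 0.15 and the arm 2 MPR proportion of 0.35", "when the sample size is 30 in each arm". With pooled rate 0.25:
- null SE = √(2 × 0.25 × 0.75/30) = 0.1118
- alternative SE = √(0.15 × 0.85/30 + 0.35 × 0.65/30) = 0.1088
- power = Φ[(0.20 − 0.8416 × 0.1118)/0.1088] = Φ(0.97) = 0.835

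The stated 83% reproduces. Exact enumeration of the uncorrected chi-square gives power 0.850 and, with 15% in both arms, one-sided error 0.210. These are the baselines below.

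**2. How often stage is unbalanced.** The documents give no stage mix for this trial, so I assume 30-50% stage IIIA. A 20-point difference is 6 of 30 patients. With the stage IIIA count in each arm binomial (30, p), the chance of a difference of at least 6 in either direction is 12.0% at p = 0.30 and 15.5% at p = 0.50. Fixing the total number of stage IIIA patients among the 60 gives 7% for 15 (where the smallest qualifying difference is 7 patients), 17% for 20, 19% for 24 and 20% for 30.

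**3. What an imbalance does.** The MPR difference shifts by imbalance × MPR gap between stages. The documents give no MPR by stage, so I assume a stage IIIA versus I-II odds ratio of 0.33 to 3, with overall MPR held at 15%. At p = 0.50 and odds ratio 0.33, the stage rates are 21.6% (I-II) and 8.4% (IIIA), a gap of 13.2 points. For a 20-point excess of stage IIIA in Arm 1:
- shift = 0.20 × 0.132 = 0.026
- null SE = √(2 × 0.15 × 0.85/30) = 0.092
- shift/SE = 0.29
- one-sided error ≈ 1 − Φ(0.84 − 0.29) = 0.29
- with the association reversed (odds ratio 3), ≈ 1 − Φ(0.84 + 0.29) = 0.13

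**4. Simulation** (200,000 trials per scenario, MPR 15% in both arms). The unadjusted test is the uncorrected chi-square. The stratified test is two-stratum Mantel-Haenszel without continuity correction. The conditional columns cover trials in which Arm 1 has at least 5 more stage IIIA patients (17 points); these are 10-12% of trials.

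| Stage odds ratio | Unadjusted, all trials | Unadjusted, unbalanced trials | Stratified, unbalanced trials |
|---|---|---|---|
| 0.33 | 0.21 | 0.29-0.31 | 0.21 |
| 0.5 | 0.21 | 0.26-0.27 | 0.20-0.21 |
| 1 | 0.21 | 0.21 | 0.20-0.21 |
| 2 | 0.21 | 0.15 | 0.20 |
| 3 | 0.21 | 0.12-0.13 | 0.21 |

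Ranges run over 30% and 50% stage IIIA. Across repeat simulations the extremes fall between 0.11 and 0.32, which is the range I quote.

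**5. Power at 15% versus 35%.**
- Unadjusted chi-square: 0.850
- Mantel-Haenszel with unstratified blocks: 0.838 if stage is unrelated to MPR, rising to 0.849 within the assumed odds-ratio range
- Mantel-Haenszel with blocks generated within stage: 0.847-0.858

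**6. Room in the model.** Expected MPR events are 30 × 0.15 + 30 × 0.35 = 4.5 + 10.5 = 15. That supports arm plus one binary stage term and no more.

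**The case against.** The strongest reply is that nothing here is invalid. Randomisation guarantees the unadjusted test's error on average, and the second column of the table confirms it: 0.21 at every odds ratio. A reader might infer from the missing stage term that the primary comparison is biased or its type I error inflated. The documents and the arithmetic do not support that. Chance imbalance is already inside the stated error rate, and this objection stands in full.

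A reader might also infer that the plan itself treats stage as a predictor of MPR, because Section 11.1.2 sets aside other trials as benchmarks since "approximately 20-25% of patients enrolled had stage IIIA disease". That remark concerns the choice of a historical disease-free survival (DFS) rate, is one of two reasons given, and says nothing about pathological response. The documents contain no link between stage and MPR. The response predictor they do discuss is PD-L1 expression, but PD-L1 is not required for eligibility and tissue is only stored for later testing (Section 5.1). Stage is the variable in hand at randomisation.

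It is also fair to say that the logistic model is not the primary test. Adding stage to it alone would leave the chi-square or Fisher comparison unchanged, so the fix has to reach the test. That the model contains only arm is read from silence: no covariate is named.

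Finally, a simple two-proportion test matching the power calculation is defensible in a 60-patient phase II trial. What survives is narrower: stage is free to use, the conditional error can move, and the plan has no agreed response if the arms turn out unbalanced.

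**Conclusion.** The point holds as a low-priority improvement. The plan leaves a known baseline variable out of both the allocation and the analysis, and has no pre-specified remedy if the arms differ in stage. The consequence is conditional on the allocation obtained. A gap of 20 points or more arises in about 12-16% of trials, a minority and not the usual case. In trials where Arm 1 has at least 17 points more stage IIIA, the unadjusted one-sided error runs from about 0.11 to 0.32, against 0.20-0.21 for a stratified test.

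This rests on two assumptions that the documents do not supply: 30-50% stage IIIA, and a stage-MPR odds ratio of 0.33 to 3. At odds ratios of 0.5 to 2 the range narrows to about 0.15-0.27, and with no association the imbalance is harmless. The figures are for the uncorrected chi-square. Fisher's exact test starts from a lower overall error (0.11 at 15% in both arms) and lower power (0.77).

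The point does not extend to the main DFS hypothesis, which compares the pooled 60 patients with a fixed 75% and does not depend on balance between arms.

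**What to change.** - **Randomisation (4.2).** For patients still to be randomised, generate the blocks of 4 within clinical stage, I-II versus IIIA. Each stratum can then end at most 2 patients out of balance. State how a patient with two primaries, whom Section 3.1 allows, is assigned to a stratum. While editing, correct the statement that blocking serves the secondary aim, since the randomised MPR comparison is now primary.
- **Analysis (11.2.1, 11.2.2).** Pre-specify a stage-stratified Mantel-Haenszel test for MPR and for clinical response in place of the unadjusted chi-square or Fisher test. Include one binary stage term in the logistic model. Report the unadjusted result and the stage distribution by arm alongside.
- **Optional.** Stratify the exploratory log-rank comparison of DFS by stage.

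The change needs no extra patients or data, but it is not free. If only the analysis changes and stage is unrelated to MPR, power falls by about 1 point (0.838 against 0.850). With stratified blocks the difference is near zero (0.847-0.858). The odds ratio also becomes conditional on stage and will not in general equal the unadjusted one, so the plan should say which is being reported. If randomisation is already complete, the analysis part still applies, provided it is fixed before MPR is compared between arms.

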1.2 Secondary Objectives

- To determine whether pre-operative anti-PDL-1 therapy with or without radiation leads to an improvement in DFS in patients with clinical stage I (tumors > 2 cm), II, and IIIA NSCLC from a historical control rate of 75% at 2 years to 89%.
- To determine if non-ablative doses of radiotherapy given concurrently with neo-adjuvant durvalumab will lead to a clinical response rate of 35% compared to a clinical response rate of 15% predicted in the antibody alone arm. The response rate of 15% selected for the antibody alone arm is consistent with response rates with durvalumab in patients with advanced refractory lung cancer.
- To determine the safety of 2 cycles of preoperative durvalumab with and without radiation followed by surgery and adjuvant durvalumab every 4 weeks for 12 cycles post-operatively.

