7.2 Assessment of safety parameters

7.2.1 Adverse Event Characteristics

CTCAE term (AE description) and grade: The descriptions and grading scales found in the revised NCI Common Terminology Criteria for Adverse Events (CTCAE) version 4.0 will be utilized for AE reporting. A copy of the CTCAE version 4.0 can be downloaded from the CTEP web site (<http://ctep.cancer.gov>).

Attribution of the AE:

- Definite – The AE is clearly related to the study treatment.
- Probable – The AE is likely related to the study treatment.
- Possible – The AE may be related to the study treatment.
- Unlikely – The AE is doubtfully related to the study treatment.
- Unrelated – The AE is clearly NOT related to the study treatment.

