7.3 Recording of Adverse Events

All adverse events will be recorded on a patient specific adverse event log. The AE log will be maintained by the research staff and kept in the patient's research chart.

Adverse events will be recorded using a recognized medical term or diagnosis that accurately reflects the event. Adverse events will be assessed by the investigator for severity, relationship to the investigational product, possible etiologies, and whether the event meets criteria of an SAE and therefore requires immediate notification to AstraZeneca/MedImmune Patient Safety.

The following variables will be collected for each AE:

- AE (verbatim)
- The date when the AE started and stopped
- Changes in NCI CTCAE grade and the maximum CTC grade attained

- Whether the AE is serious or not
- Investigator causality rating against durvalumab (yes or no)
- Action taken with regard to durvalumab
- Outcome

In addition, the following variables will be collected for SAEs as applicable:

- Date AE met criteria for serious AE
- Date Investigator became aware of serious AE
- Reason AE is serious
- Date of hospitalization
- Date of discharge
- Probable cause of death
- Date of death
- Autopsy performed
- Description of AE
- Causality assessment in relation to Study procedure(s)

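### Attribution scale (7.2.1), adverse event variable list (7.3) and toxicity table (11.2.2) do not fit together, and a non-serious grade 3 or higher event due to SBRT alone has no related category

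*Combined protocol and SAP*

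**What the plan says.** The safety objective in Section 1.2 begins "To determine the safety of 2 cycles of preoperative durvalumab with and without radiation". By Section 5.1, both arms receive two preoperative cycles of durvalumab, and Arm 2 adds three 8 Gy fractions of SBRT with the first cycle.

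Attribution is dealt with in several places:

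- **Section 7.2.1** sets five levels: Definite, Probable, Possible, Unlikely, Unrelated. The top level reads "The AE is clearly related to the study treatment".
- **Section 7.3** lists the variables for each adverse event. The one causality item is "Investigator causality rating against durvalumab (yes or no". For serious events it adds "Causality assessment in relation to Study procedure(s".
- **Section 7.1.2** asks for the causality of serious events against every study treatment and procedure.
- **Section 7.3.3** counts definite and probable events as study-related for IRB reporting.
- **Section 11.2.2** opens its toxicity analysis with "All AEs in both arms" of grade 3 or higher, which "with and without possible or probable attribution to study drug will be tabulated". It continues: "The frequency of subjects experiencing toxicities will be tabulated for each arm". It also plans intervals: "Exact 95% confidence intervals around the toxicity proportions will be calculated to assess the precision of the obtained estimates".

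**The concern.** The table in 11.2.2 needs an attribution variable, and the plan describes two that differ in scale and in object. One is a five-level rating against study treatment. The other is a yes/no rating against durvalumab. The table uses neither as defined: it takes two of the five levels and points them at study drug.

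What is at stake is the meaning of the attributed rows. SBRT is the only planned difference between the arms, and Section 7.1.12 expects it to carry minimal or no risk. Attributed rows that cannot record an event as SBRT-related can neither support nor contradict that expectation. Sections 6.1 and 7.1.3 also direct investigators to look for other causes before calling an event immune-related. In Arm 2, radiation is one such cause, for instance for pneumonitis, which is a listed event of special interest. In this open-label trial the same event could therefore be rated yes against durvalumab in Arm 1 and no in Arm 2.

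**Working it through.** The plan states no figure on this point, so there is none to reproduce. The check sets the sections side by side and follows each kind of event through them.

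**Step 1. Scale and object in each section**

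| Section | Scale | Rated against | Events covered |
|---|---|---|---|
| 7.2.1 | five levels, including Definite | study treatment | adverse events |
| 7.3, all-event list | yes/no | durvalumab | every adverse event |
| 7.3, serious-event list | not stated | study procedures | serious events |
| 7.1.2 | not stated | all study treatment and procedures | serious events |
| 11.2.2 | possible or probable | study drug | grade 3 or higher |

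The 11.2.2 table is defined by grade, not by seriousness. A grade 3 event that meets no seriousness criterion enters the table, but the wider causality requirement for serious events does not reach it.

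**Step 2. If the 7.3 yes/no field feeds the table**

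- Definitely due to durvalumab: recorded yes, counted as attributed. Nothing is lost.
- Possibly or probably due to durvalumab: the field cannot tell the two levels apart.
- Non-serious and due to SBRT alone: recorded no, placed in the unattributed rows. This can happen only in Arm 2.

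**Step 3. If the 7.2.1 five-level scale feeds the table**

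- Definite: read literally, this is outside possible or probable, so it falls in the unattributed rows. This applies to both arms.
- Due to SBRT alone: it can be rated as related if study treatment includes SBRT. However, one rating against the combined treatment does not identify the component, and 11.2.2 asks about study drug.

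The loss of Definite belongs to Step 3 and the durvalumab-only recording to Step 2. They do not both follow from one data source and should not be added together.

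**Step 4. Size per patient**

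Section 11.1.1 gives 30 patients per arm. One reclassified patient moves a proportion by 1/30 = 3.3 percentage points.

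For illustration only, assume that 6 of 30 Arm 2 patients truly have a related grade 3 or higher event. The exact 95% limits for x of n are the 0.025 quantile of Beta(x, n − x + 1) and the 0.975 quantile of Beta(x + 1, n − x), with n = 30:

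| Patients moved to unattributed | Attributed rate | Exact 95% interval |
|---|---|---|
| 0 | 6/30 = 20.0% | 7.7% to 38.6% |
| 1 | 5/30 = 16.7% | 5.6% to 34.7% |
| 2 | 4/30 = 13.3% | 3.8% to 30.7% |
| 3 | 3/30 = 10.0% | 2.1% to 26.5% |

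The total of attributed and unattributed events is the same in every row.

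**The case against.** The strongest reply is that the SBRT safety question is answered without attribution. All grade 3 or higher events are tabulated whether attributed or not, and toxicity frequency is given by arm with no attribution filter stated. The all-cause comparison of randomised arms is the better evidence on added toxicity, and it is intact. The plan attaches no test, threshold or decision rule to related toxicity, and the Section 7.4 stopping rule counts postoperative deaths regardless of cause. All of this stands, and it confines the point to one descriptive split.

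Three stronger readings are tempting, and the documents do not support them:

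- **That causality is collected for durvalumab alone.** Section 7.2.1 rates against study treatment. Sections 7.1.2 and 7.3 widen causality for serious events. Section 7.3 also has the investigator consider possible etiologies for every event. The case report form is not in the documents, so it cannot be said that the five levels go unrecorded. What can be said is that the all-event list names only durvalumab and has no SBRT item.
- **That events drop out and Arm 2 toxicity is understated overall.** No event leaves the safety analysis. Omitting Definite affects both arms; only the SBRT gap is specific to Arm 2.
- **That every definite event is certain to be lost.** Possible or probable may be meant as a floor: Section 7.4 speaks of events at least possibly related, and Section 7.3.3 treats definite as related. Under the yes/no field the loss does not arise.

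The reply does not make the three sections consistent, and it does not give a non-serious SBRT-only event a related category.

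**Conclusion.** The concern holds in a limited form. The scale, the collection list and the tabulation rule are mutually inconsistent. Followed as written, the attributed rows omit Definite in both arms if the five-level scale is used. A non-serious grade 3 or higher event judged due to SBRT alone has no place among related events. The second gap can lower the related-toxicity rate in Arm 2, in those rows only.

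The size cannot be estimated, because the documents give no expected counts of definite or SBRT-only events; the 6 of 30 used above is an assumption. The conclusion rests on taking 7.3 as the list of what is collected and 11.2.2 as literal. If the form holds more than 7.3 lists, or the analyst counts Definite as related, part of the problem disappears in practice, but the plan should say so. It merits correction because the safety aim is durvalumab with and without radiation, and the attributed rows do not see the radiation.

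**What to change.** - **Section 7.3:** for every adverse event, serious or not, record attribution on the 7.2.1 five-level scale separately for durvalumab, for SBRT, and for surgery or procedure.
- **Section 11.2.2:** define related as definite, probable or possible to durvalumab or SBRT. Report related events by component and by arm beside the all-cause table, which stays as planned.

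The cost is one or two fields on the adverse event form and one sentence in 11.2.2. It is best done early, because an investigator's judgement at the time of the event is hard to reconstruct later.
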